**Table 1: Study Objectives (Continued)**

**Table 2: Study Endpoints**

Endpoint	Name	Description	Timeframe
Phase 1b Dose-finding and AG-120 Expansion Stage			
Primary	Recommended Combination Dose	Review of dose-limiting toxicities (DLTs), safety, PK / pharmacodynamic, biomarker, and preliminary efficacy data by DRT.	Approximately 8 months
	Safety / tolerability	Type, frequency, seriousness and severity of AEs, and relationship of AEs to study treatment.	Approximately 13 months
Secondary	Overall Response Rate (as assessed by the investigator)	Rate of CR + CRi + CRp + MLFS + PR according to modified IWG AML response criteria ( Appendix F ).	Approximately 13 months
	Sponsor Derived CR and CRh	Rate of CR/ CRh and CR + CRh based on laboratory data	Approximately 13 months

**Table 2: Study Endpoints (Continued)**

Endpoint	Name	Description	Timeframe
Primary	Overall Response Rate (as assessed by the investigator)	Rate of CR + CRi + CRp + MLFS + PR according to modified IWG AML response criteria ( Appendix F ).	Approximately 30 months
Secondary	Event-Free Survival	Time from randomization to documented morphologic relapse, progression according to modified IWG AML response criteria ( Appendix F ), or death from any cause, whichever occurs first.	Approximately 30 months
	Safety / tolerability	Type, frequency, seriousness and severity of AEs, and relationship of AEs to study treatment.	Approximately 30 months
	Complete remission rate	Rate of CR according to modified IWG AML response criteria ( Appendix F ).	Approximately 30 months
	Sponsor Derived CR	Rate of CR based on laboratory data	Approximately 30 months
	Sponsor Derived CR and CRh	Rate of CR +CRh based on laboratory data	Approximately 30 months
	Hematologic improvement rate	Rate of HI-N + HI-P + HI-E according to IWG MDS HI criteria ( Appendix G ).	Approximately 30 months
	Duration of Response	Time from the first documented MLFS/CR/CRi/CRp/PR to documented morphologic relapse, progression according to modified IWG AML response criteria ( Appendix F ), or death due to any cause, whichever occurs first	Approximately 30 months
	Time to response	Time from first dose of study drug to first documented CR/CRi/CRp/MLFS/PR according to modified IWG AML response criteria ( Appendix F )	Approximately 30 months
	Time to sponsored assessed CR and CRh	Time from first dose of study drug to first documented CR / CRh	Approximately 30 months
	Duration of sponsor assessed CR and CRh	Time from the first documented CR/CRh to documented morphologic relapse, progression	Approximately 30 months
Overall Survival	Time from randomization to death due to any cause.	Approximately 30 months	

**Table 2: Study Endpoints (Continued)**

Endpoint	Name	Description	Timeframe
	One-year survival	The probability of survival at 1 year from randomization	Approximately 30 months
	PK parameters	Plasma concentrations and pharmacokinetic parameters of AG-221.	Approximately 30 months
	HRQoL outcomes	European Organization for Research and Treatment of Cancer Quality-of-Life questionnaire (EORTC QLQ-C30) ( Appendix N ) and EuroQoL Group EQ-5D-5L instrument ( Appendix O )	Approximately 30 months

Abbreviations: [REDACTED] AE = adverse event; AML = acute myeloid leukemia; [REDACTED] CR = morphologic complete remission; CRh = morphologic complete remission with partial hematologic recovery; CRi = morphologic complete remission with incomplete neutrophil recovery; CRp = morphologic complete remission with incomplete platelet recovery; DRT = Dose Review Team; EORTC= European Organization for Research and Treatment of Cancer; HI = hematologic improvement; HI-E = hematologic improvement erythroid response; HI-N = hematologic improvement neutrophil response; HI-P = hematologic improvement platelet response; HRQoL = Health-related Quality-of-Life; IWG = International Working Group; MDS = myelodysplastic syndrome; MLFS = morphologic leukemia-free state; [REDACTED] PK = pharmacokinetics; PR = partial remission; SC = subcutaneous.

### 3. OVERALL STUDY DESIGN

#### 3.1. Study Design

This Phase 1b/2 study is an open-label, randomized, multicenter trial to evaluate the safety and efficacy of oral AG-120 + SC azacitidine and oral A-221 + SC azacitidine in subjects with newly diagnosed AML with an IDH1 or an IDH2 mutation, respectively. The study population consists of subjects who are not candidates to receive intensive IC. The study comprises a Phase 1b dose-finding and AG-120 expansion stage and a Phase 2 randomized stage.

##### **Phase 1b Dose-finding Stage**

The Phase 1b segment is a combination dose-finding study to identify the RCD of oral AG-120 + SC azacitidine in subjects with an IDH1 mutation or oral AG-221 + SC azacitidine in subjects with an IDH2 mutation. Subjects are considered eligible for this trial if they have newly diagnosed AML and present with co-morbidities, declining performance status, or other factors that in the investigators judgment make them not candidates to receive intensive IC. The Phase 1b segment will evaluate the safety and clinical activity of oral AG-120 or AG-221 administered with SC azacitidine in this population. For the AG-120 combination, upon declaration of the RCD by the DRT, an AG-120 expansion cohort of up to 15 patients will be enrolled at RCD for further safety evaluation and PK sampling.

The Phase 1b dose-finding segment will use a standard “3 + 3” design. Each dose cohort will enroll a minimum of 3 subjects. Study drug will start on Cycle 1 Day 1 (C1D1) at which time daily dosing will begin for AG-120 and AG-221 for days 1-28 of each 28-day cycle. Azacitidine will be administered SC for 7 days of each 28-day cycle starting at Cycle 1 Day 1. If there are multiple subjects in the screening process at the time the third subject within a cohort begins treatment, up to 2 additional subjects may be enrolled with documented approval of the medical monitor.

The safety of dosing during Phase 1b will be evaluated by the DRT (Celgene medical monitor, Celgene lead safety physician, Celgene biostatistician, other Celgene functional area representatives or designees, as appropriate and all active site investigators and/or designees (at sites with a subject who has received study drug). The DRT will review the emerging safety data from each cohort.

##### DLT-evaluable Subjects

Dose Determining Set (DDS): Subjects who take at least one dose of study drug in Phase 1b dose-finding stage and either have a DLT during Cycle 1 regardless of amount of study drug exposure, or have no DLT and complete at least 75% of AG-120 or AG-221 doses (21 out of 28 days) and a minimum of 5 doses of azacitidine, and at least 50% of the planned combination doses for AG-120 or AG-221 and azacitidine administered together (in the same day for 4 out of 7 days) in the first 28 days from Cycle 1 Day 1 and are also considered by the Clinical Study Team to have sufficient safety data available to conclude that a DLT does not occur during Cycle 1. A subject diary will be used during outpatient treatment to record details around AG-120 and AG-221 dosing.

### Safety Evaluation for Combination Therapy

This study will use a standard “3 + 3” design for AG-120 and AG-221 dose determination, identifying the RCD dose level. Each dose cohort will plan to enroll 3 DLT-evaluable subjects, starting with Dose Level 1. Dose escalation or de-escalation decisions will be made independently for each IDH inhibitor + SC azacitidine therapy. For AG-120, there is no dose escalation, but 1 dose de-escalation is allowed to Dose Level -1. For AG-221, there is 1 dose escalation to Dose Level 2 and 1 dose de-escalation to Dose Level -1. Due to the lack of overlapping toxicities, azacitidine will be administered, by the site staff, at 75 mg/m^2 dose for 7 days of the 28 day cycle. The DRT will review all safety data available for each cohort to determine whether a dose adjustment of azacitidine is warranted for the combination.

#### **Phase 1b AG-120 Expansion Stage**

An expansion cohort of approximately 15 IDH1 patients will be enrolled to the AG-120 combination (Section 3.1.1.4). Subjects enrolled in the AG-120 expansion will receive the AG-120 + azacitidine at the RCD.

#### **Phase 2 Randomized Stage**

The Phase 2 segment of the study is an open label, randomized, 2-arm design to evaluate the efficacy and safety of oral AG-221 with SC azacitidine versus SC azacitidine alone. Eligible subjects must have newly diagnosed AML with an IDH2 mutation and, who are not candidates to receive intensive IC based on the investigators assessment.

All subjects discontinued from study treatment for any reason other than withdrawal of consent for follow-up will continue to be assessed for AEs, concomitant medications, concomitant procedures, transfusions, [REDACTED] response, hematologic improvement, subsequent AML therapies, and survival.

- All subjects discontinued from study treatment for any reason except withdrawal of consent for follow-up or disease progression will continue to be assessed during the Follow-up period of the study for response until disease progression (Section 6.3).
- All subjects discontinued from study treatment for any reason except withdrawal of consent for follow-up will continue to be assessed for subsequent AML therapies, and survival (Section 6.3).

The trial will continue until enough EFS events to allow full statistical analysis (Section 9).

See [Figure 3](#): Overall Study Design Phase 1b and [Figure 4](#): Overall Study Design Phase 2.

#### **3.1.1. Phase 1b Dose-finding and AG-120 Expansion Stage**

The Phase 1b segment of the study will consist of Screening, Treatment, and Follow-up periods.

The dose finding will use a “3 + 3” design ([Figure 3](#)). Each dose cohort will plan to enroll 3 subjects. Both investigational products will be started on Cycle 1 Day 1 (C1D1).

In the AG-120 dose-finding arm, a minimum of 3 eligible subjects with an IDH1 mutation will be enrolled into Cohort 1 with oral AG-120, 500 mg daily and azacitidine 75 mg/m^2/day SC for 7 days of each 28-day cycle starting on Day 1 of each cycle. If none of the 3 subjects has a DLT then the RCD will be confirmed by the DRT. An additional 3 subjects will be enrolled if 1

subject has a DLT. If 2 or more DLTs are declared in Cohort 1, then Cohort -1 will be explored with AG-120 at a dose of 250 mg daily and azacitidine 75 mg/m^2/day SC for 7 days of each 28-day cycle (Table 3). If a cohort is expanded to six subjects due to a DLT the RCD will be declared by the DRT at the dose level where no more than 1 of six subjects experiences a DLT (Figure 1). Upon declaration of the RCD by the DRT an AG-120 expansion cohort of up to 15 patients will be enrolled for further safety evaluation and PK sampling.

For AG-221 two dose levels will be explored. Three eligible subjects with an IDH2 mutation will be enrolled into Cohort 1 and receive oral AG-221, 100 mg daily and azacitidine 75 mg/m^2/day SC for 7 days of each 28-day cycle starting on Day 1 of each cycle. If no DLTs are observed in a cohort of 3 subjects, or no more than 1 DLT in an expanded cohort of 6 subjects experience a confirmed DLT the RCD will be confirmed by the DRT and the 100 mg dose will be used as the starting dose for the Phase 2 segment of the study. Dose escalation to Cohort 2 will be initiated with oral AG-221 200 mg once a day and azacitidine 75 mg/m^2/day SC for 7 days of each 28-day cycle starting on Day 1 of each cycle to explore the tolerability of the combination at this dose level. If 2 or more subjects in the expanded Cohort 1 experience a DLT, Cohort -1 with oral AG-221 50 mg daily and azacitidine 75 mg/m^2/day SC for 7 days of each 28-day cycle starting on Day 1 of each cycle will be explored and no escalation to Cohort 2 or dose escalation to a 200 mg dose will be used in Phase 2 of this study (Figure 2).

The RCD will be declared as Cohort -1 if no DLTs are observed in a cohort of 3 subjects, or no more than 1 DLT in an expanded cohort of 6 subjects.

If enrollment is initiated in Cohort 2 and no DLTs are observed in a cohort of 3 subjects, or no more than 1 DLT in an expanded cohort of 6 subjects, the data will be reviewed by the DRT for potential dose escalation during Phase 2 to augment treatment response.

**Table 3: Phase 1b Dose Cohorts**

Cohort	IDH1		IDH2	
	AG-120	Azacitidine	AG-221	Azacitidine
Cohort -1	250 mg QD for 28 days	75 mg/m  /day SC for 7 days of each 28-day cycle	50 mg QD for 28 days	75 mg/ m  /day SC for 7 days of each 28-day cycle
Cohort 1	500 mg QD for 28 days	75 mg/m  /day SC for 7 days of each 28-day cycle	100 mg QD for 28 days	75 mg/ m  /day SC for 7 days of each 28-day cycle
Cohort 2	NA	NA	200 mg QD for 28 days	75 mg/ m  /day SC for 7 days of each 28-day cycle

The DRT will review all toxicities following the completion of Cycle 1 of each cohort to determine whether dose modification of azacitidine is warranted or additional cohorts are needed to further assess the safety of the combination.

### 3.1.1.1. 3 + 3 Design

The 3 + 3 design allows for the enrollment of three subjects concurrently, with IDH1 or IDH2 mutations, into their respective Cohort 1. Local confirmation of the primary malignancy is required. Subjects in the dose-finding phase are required to have IDH1 or IDH2 gene-mutated disease, documented by local site testing.

The dose-finding phase will use a standard “3 + 3” design. During the dose-finding phase, eligible subjects with an IDH 1 mutation will be enrolled into one cohort of AG-120, or for subjects with an IDH2 mutation, sequential cohorts of increasing doses of AG-221. Each dose cohort will plan to enroll a minimum of 3 subjects. A cohort will be expanded to 6 subjects if one of the initial 3 subjects experiences a DLT. If there are multiple subjects in the screening process at the time the third subject within a cohort begins treatment, up to 3 additional subjects may be enrolled, for a maximum of 6 subjects per cohort, with documented approval of the Medical monitor.

An expansion cohort of approximately 15 IDH1 patients will be enrolled to the AG-120 combination (Section 3.1.1.4).

Schematics for the dose finding for doses of AG-120 and AG-221 are provided in [Figure 1](#) and [Figure 2](#).

#### AG-120

The safety of dosing will be evaluated by the DRT comprised of the Celgene medical monitor, Celgene lead safety physician, Celgene biostatistician, other Celgene functional area representatives or designees, as appropriate, and all active site investigators and/or designees (at sites with a subject who has received study drug). The DRT will review the emerging safety data from the cohort to determine whether dose de-escalation will occur.

#### *AG-120 Cohort 1*

If, after the third subject in Cohort 1 completes the 28-day DLT evaluation period (ie, Cycle 1), no DLTs (Section 3.1.1.3) are observed, Cohort 1 will be declared the RCD following review by the DRT.

If 1 of 3 subjects experiences a DLT during the first cycle, 3 additional subjects will be enrolled in that cohort. If none of the additional 3 subjects experience a DLT, the RCD will be confirmed following review by the DRT.

#### *AG-120 de-escalation from Cohort 1 to Cohort -1*

If 2 or more subjects in Cohort 1 experience DLTs during the first cycle, dose escalation will be halted and the next lower dose level (Cohort -1) will be explored. If no DLTs are observed, Cohort -1 will be declared the RCD by the DRT.

[figure not shown]
If 1 of 3 subjects experiences a DLT in Cohort -1, 3 additional subjects will be enrolled in that cohort. If none of the additional 3 subjects experience a DLT, the expanded Cohort 1 will be declared the RCD and will be confirmed following DRT review.

If 2 or more subjects in Cohort -1 experience DLTs during the first cycle, dosing will be halted and all data will be reviewed by the DRT.

Note that if a given cohort initially enrolled 4 or 5 subjects (ie, if there were multiple subjects in the screening process at the time the third subject within a cohort began treatment), the same rules for dose de-escalation apply. If 1 of the 4 (or 5 subjects) experiences a DLT, the cohort will be expanded to include a total of 6 subjects, and will be halted if 2 or more subjects experience a DLT.

The study will be conducted in compliance with the International Council for Harmonization (ICH) of Technical Requirements for Registration of Pharmaceuticals for Human Use/Good Clinical Practice (GCP) and applicable regulatory requirements.

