During the treatment period a standard 3 + 3 design will be used (Section 3.1.1). A Dose Review Team (DRT), consisting of a Celgene medical monitor, Celgene lead safety physician, Celgene biostatistician, other Celgene functional area representatives or designees, as appropriate, and all active site investigators and/or designees (at sites with a subject who has received study drug), will review all adverse events (AEs) experienced by subjects during Cycle 1 of each dose level to determine whether the maximum tolerated dose (MTD) of oral AG-120 or AG-221 when administered with SC azacitidine has been exceeded. One dose level of oral AG-120 (500 mg daily) and 2 dose levels of oral AG-221 (100 mg daily and 200 mg daily) are planned to be evaluated. Dose levels lower than 500 mg daily for oral AG-120 and lower than 100 mg daily for oral AG-221 will be evaluated if these doses when administered with SC azacitidine are found to exceed the MTD during Cycle 1. Dose interruptions/delays and dose reductions may be used to manage toxicities. Subjects may receive study treatment until disease progression/relapse, study treatment becomes intolerable, or the subject wishes to discontinue study treatment for any reason. Response to treatment will be assessed by the investigators according to the modified International Working Group (IWG) AML Response Criteria (Cheson, 2003) (Appendix F). Hematologic improvement (HI) in subjects with newly diagnosed AML will also be assessed according to the IWG myelodysplastic syndromes HI criteria (Cheson, 2006) (Appendix G). Subjects are to undergo end-of-treatment evaluations when study treatment is discontinued (Section 3.1.2.3). The reason for treatment discontinuation will be recorded in the electronic case report form (eCRF) pages and in the source document.

All subjects discontinued from study treatment for any reason other than withdrawal of consent for follow-up will continue to be assessed for AEs, concomitant medications, concomitant procedures, transfusions, [REDACTED] response, hematologic improvement, subsequent AML therapies, and survival.

- All subjects discontinued from study treatment for any reason except withdrawal of consent for follow-up or disease progression will continue to be assessed during the Follow-up period of the study for response until disease progression (Section 6.3).

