### *AG-221 de-escalation from cohort 1 to cohort -1*

If 2 or more subjects in cohort 1 experience DLTs during the first cycle, dose escalation will be halted and following review by the DRT, the next lower dose level (cohort -1) will be explored. If no DLTs are observed (see 3.1.1.3) cohort -1 will be declared the RCD following DRT review.

[figure not shown]
If 1 of 3 subjects experiences a DLT in cohort -1, 3 additional subjects will be enrolled in that cohort. If none of the additional 3 subjects experience a DLT in the expanded cohort -1 it will be declared the RCD will be confirmed following DRT review.

If 2 or more subjects in cohort -1 experience DLTs during the first cycle, dosing will be halted and all data will be reviewed by the DRT.

Note that if a given cohort initially enrolled 4 or 5 subjects (ie, if there were multiple subjects in the screening process at the time the third subject within a cohort began treatment), the same rules for dose escalation apply. If 1 of the 4 (or 5 subjects) experiences a DLT, the cohort will be expanded to include a total of 6 subjects; dose escalation will occur if only 1 of 6 subjects experiences a DLT and will be halted if 2 or more subjects experiences a DLT.

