## **7.2.1. Treatment Administration**

### **7.2.1.1. Dispensation and Administration of AG-120 or AG-221**

#### Phase 1b Dose-finding and AG-120 Expansion Stage

AG-120 given at 500 mg in cohort 1 or 250 mg in cohort -1, orally QD on Days 1 – 28 of each 28-day cycle until treatment discontinuation (Section 11.1).

AG-221 is given at 100 mg in cohort 1, 200 mg in cohort 2, or 50 mg in cohort -1, orally QD on Days 1 – 28 of each 28-day cycle until treatment discontinuation (Section 11.1).

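### One branch of the AG-120 3+3 rule names Cohort 1 (500 mg) as the recommended dose where the protocol's own rules select Cohort -1 (250 mg)

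*Protocol*

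**What the plan says.** Section 7.2.1.1 of the Protocol fixes the doses: "AG-120 given at 500 mg in cohort 1 or 250 mg in cohort -1". The Protocol Summary says that lower doses than the planned ones "will be evaluated if these doses when administered with SC azacitidine are found to exceed the MTD during Cycle 1".

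The AG-120 de-escalation text in Section 3.1.1.1 then runs as follows.

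- Entry to the branch: "If 2 or more subjects in Cohort 1 experience DLTs during the first cycle, dose escalation will be halted", and the next lower level, Cohort -1, is explored.
- One DLT at the lower level: "If 1 of 3 subjects experiences a DLT in Cohort -1, 3 additional subjects will be enrolled in that cohort".
- Outcome of that expansion: "If none of the additional 3 subjects experience a DLT, the expanded Cohort 1 will be declared the RCD", subject to confirmation after DRT review.

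The general AG-120 rule for a cohort expanded to six is in Section 3.1.1: "the RCD will be declared by the DRT at the dose level where no more than 1 of six subjects experiences a DLT". For AG-221, the corresponding sentence in Section 3.1.1.1 is: "If none of the additional 3 subjects experience a DLT in the expanded cohort -1 it will be declared the RCD".

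**The concern.** The branch exists because 500 mg has shown too many DLTs. A good result at 250 mg should therefore recommend 250 mg. The printed sentence sends the recommendation back to 500 mg.

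The RCD is a Phase 1b primary endpoint (Protocol Table 2), and Section 7.2.2.1.2 makes it the dose for the AG-120 expansion cohort of up to 15 subjects. Had this branch been reached and the text followed, the expansion would have been dosed at a level already over its DLT limit.

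**Working it through.** The protocol states no figure for this point, so the check is a trace of the rule, followed by the arithmetic that the rule implies.

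**Step 1: what must have happened in Cohort 1 (500 mg).** The branch requires at least 2 DLTs there. The possible routes are:

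| Route | Minimum observed DLT rate |
|---|---|
| At least 2 among the first 3 | 2/3 = 67% |
| At least 2 among 4 initially enrolled | 2/4 = 50% |
| At least 2 among 5 initially enrolled | 2/5 = 40% |
| 1 of 3, then at least 1 of the next 3 | 2/6 = 33% |

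The lowest rate compatible with entering the branch is 33%. Every route breaks the limit of 1 in six.

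**Step 2: what happened in Cohort -1 (250 mg).** 1 of 3, then 0 of 3, gives 1 of 6 = 17%. This meets the limit.

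**Step 3: compare each Cohort -1 outcome with the governing rule.**

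| Cohort -1 result | AG-120 de-escalation text | Rule in Section 3.1.1 |
|---|---|---|
| 0 of 3 | Cohort -1 is the RCD | Not expanded, so the six-subject rule is not engaged |
| 1 of 3, then 0 of 3 | Expanded Cohort 1 is the RCD | Cohort -1 (1 of 6); Cohort 1 is excluded (at least 2) |
| 2 or more | Dosing halted, DRT review | No level qualifies |

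Only the middle row conflicts. The cohort being expanded there is Cohort -1, as the preceding sentence states. If Cohort 1 failed within its first 3 subjects, it was never expanded, and the sentence refers to a cohort that does not exist.

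**Step 4: size of the discrepancy, with no DLT rates assumed.**

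- Dose: 500/250 = 2 times.
- Observed DLT rate: at least (2/6)/(1/6) = 2 times. It is at least (2/3)/(1/6) = 4 times if Cohort 1 failed in its first 3 and the sentence is still read as meaning 500 mg.

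**Step 5: how often the branch would be reached (illustration only).** The documents give no true DLT rates, so these are assumptions. With rate p at 500 mg and q at 250 mg, and 3 subjects per step:

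- P(Cohort 1 fails) = P(at least 2 of 3) + 3p(1−p)² × [1 − (1−p)³]
- P(1 of 3, then 0 of 3 in Cohort -1) = 3q(1−q)² × (1−q)³

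For p = 20% and q = 10%: 0.291 × 0.177 = 0.052, or 5.2%. Over p from 10% to 50% and q from 5% to 30%, with q never above p, the product runs from 1.1% (p = 10%, q = 5%) to 16.3% (p = 50%, q = 20%). At the design stage this was an unlikely branch, but not a negligible one.

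**The case against.** The strongest points on the other side are these.

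**The minus sign may have been lost when the PDF was read.** Hyphens do come and go in the text available to us; the QT prolongation text in Section 7.2.2.3.2 prints AG-120 both with and without one. Against this, the other five mentions of Cohort -1 under the same heading (one in the heading, four in the body) all keep the sign. An error in the source is more likely, but only the source page settles it. The intended meaning is not in doubt either way.

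**The documents already resolve the ambiguity.** Section 3.1.1 gives the right rule, the sentence itself calls for DRT review, and Section 3.1.1.2 makes the DRT responsible for dosing decisions. Figure 1, which could not be seen, may show the branch correctly. This stands as a reason why harm was unlikely. It does not make the sentence right: a DRT following it would be asked to confirm a dose that fails the six-subject rule.

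**The rule for Cohort 1's own expansion adds little.** That rule ("If none of the additional 3 subjects experience a DLT, the RCD will be confirmed following review by the DRT") concerns a Cohort 1 with 1 DLT in six and does not govern Cohort -1. This is fair; the conflict rests on Section 3.1.1 and the surrounding de-escalation text.

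**Nothing now depends on it.** SAP Section 2 lists AG-120 only at 500 mg, in both dose-finding and expansion. The latest amendment justification reports a finalized primary study report and 4 AG-120 subjects on treatment at 15 March 2021. This stands, and it limits the point to correcting the record.

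**Conclusion.** The concern holds. In one AG-120 branch the protocol recommends 500 mg where its own rules recommend 250 mg: twice the dose, with an observed DLT rate of at least 33% rather than 17%. These figures follow from the cohort rules alone.

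The remaining consequence is low. The absence of a 250 mg AG-120 arm from the SAP indicates that the branch was not reached, and no estimate, error rate, population or sample size depends on the sentence. It merits correction because it is an operative dose-selection rule, and because any study reusing this 3+3 text would inherit the error. The one reservation is whether the minus sign is missing in the sponsor's source or was lost in reading the PDF.

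**What to change.** First check the source page. If the minus sign is missing there, change Cohort 1 to Cohort -1 in that sentence, so that the expanded Cohort -1 is declared the RCD after DRT review. Confirm that Figure 1 shows the same outcome.

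The edit is one character. Under Section 13.5 even an administrative amendment needs sponsor medical approval and goes to the ethics committees for information, so it is sensible to carry the change in the next amendment made for other reasons. Nothing in the SAP, data or analyses needs to change.
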